1.1 Background and rationale

Osteoarthritis (OA) is a prominent cause of years lived with disability worldwide [1]. The hand is one of the most commonly affected sites [2] with a lifetime risk of 50% in women and 25% in men for developing hand OA (HOA) [3]. There are no disease-modifying drugs that can cure HOA. Patient education, hand exercises, and assistive devices are the core treatments, while Non-Steroid Anti-Inflammatory Drugs (NSAIDs) can be used for a limited duration to relieve symptoms [4]. Surgery should only be considered if other treatment modalities are ineffective [4]. Core treatment should primarily be provided in primary healthcare, however, research shows that the quality-of-care of OA-services in general is sub-optimal [5], and in particular for people with HOA [6,7].

The use of eHealth is highlighted for self-management and better exploitation of healthcare resources [8]. An observational study suggests that digital delivery of core treatment could be a viable option in people with HOA [9], however, large methodologically sound trials of effect and cost-effectiveness are lacking [10].

In 2020, development of the Happy Hands app was initiated at Diakonhjemmet Hospital, Norway [11], with an overarching goal of delivering a standalone intervention that supports and empowers people with HOA to self-manage their disease, regardless of where they reside [11]. Feasibility of the app has been tested in 71 patients with HOA with promising results [12], and there is now a need to test the app in an RCT to assess the effect and cost-effectiveness.

1.2 Trial Objectives

1.2.1 Primary Objective

The primary objective of this study is to assess whether a 12-week self-management intervention delivered through the Happy Hands app in addition to usual care is more effective compared to usual care alone in patients with HOA with regards to the **probability of OMERACT/OARSI response** at **3 months**.

1.2.2 Secondary Objectives

Key secondary objectives are:

- To assess whether a 12-week self-management intervention delivered through the Happy Hands app in addition to usual care is more effective compared to usual care alone in patients with HOA with regards to the **probability of OMERACT/OARSI response** at 6 months.
- To assess whether a 12-week self-management intervention delivered through the Happy Hands app in addition to usual care is cost-effective compared to usual care alone in patients with HOA at 6 months.

Statistical Analysis Plan Happy Hands Diakonhjemmet Hospital

Page 5 of 27

- To assess whether a 12-week self-management intervention delivered through the Happy Hands app in addition to usual care is more effective than to usual care alone in patients with HOA with regards to **change in pain** at **3 months**.
- To assess whether a 12-week self-management intervention delivered through the Happy Hands app in addition to usual care is more effective than to usual care alone in patients with HOA with regards to **change in hand function** at **3 months.**

Other secondary objectives are:

- To assess whether a 12-week self-management intervention delivered through the Happy Hands app in addition to usual care is more effective than to usual care alone in patients with HOA with regards to **change in grip strength** at **3 months**.
- To assess whether a 12-week self-management intervention delivered through the Happy Hands app in addition to usual care is more effective than to usual care alone in patients with HOA with regards to **change in quality of care** at **3 months**.
- To assess whether a 12-week self-management intervention delivered through the Happy Hands app in addition to usual care is more effective than to usual care alone in patients with HOA with regards to **change in disease activity** at **3 months**.
- To assess whether a 12-week self-management intervention delivered through the Happy Hands app in addition to usual care is more effective than to usual care alone in patients with HOA with regards to **change in pain** at **6 months**.
- To assess whether a 12-week self-management intervention delivered through the Happy Hands app in addition to usual care is more effective than to usual care alone in patients with HOA with regards to **change in hand function** at **6 months**.
- To assess whether a 12-week self-management intervention delivered through the Happy Hands app in addition to usual care is more effective than to usual care alone in patients with HOA with regards to **change in grip strength** at **6 months**.
- To assess whether a 12-week self-management intervention delivered through the Happy Hands app in addition to usual care is more effective than to usual care alone in patients with HOA with regards to **change in quality of care** at **6 months**.
- To assess whether a 12-week self-management intervention delivered through the Happy Hands app in addition to usual care is more effective than to usual care alone in patients with HOA with regards to **change in disease activity** at **6 months**.

1.2.3 Exploratory Objectives

- To assess the adherence, satisfaction and usability of the Happy Hands
- To identify factors associated with being an OMERACT/OARSI responder at 3 and 6 months

Statistical Analysis Plan Happy Hands Diakonhjemmet Hospital

Page 6 of 27

- To identify factors associated with adherence to the self-management intervention delivered through the Happy Hands app.

2. Trial Methods

2.1 Trial Design

The Happy Hands study is designed as a pragmatic, open-labelled, 2-armed, randomized, controlled, multicenter, single-country trial. Participants are randomly allocated to either usual care (control group) or usual care combined with use of the Happy Hands app across a 12-weeks period (intervention group).

2.3 Sample size

The sample size is calculated based on the primary outcome (proportion of OMERACT-OARSI responders) measured at 3 months. An OMERACT-OARSI responder rate between 26-46% is previously shown in hand exercise groups compared to 6-24% in usual care groups [13,14]. The between-group difference in primary outcome is estimated to 20% [15]. To account for multiple testing (primary and key secondary hypotheses), we will use a significance level of 1%, and 90% power. With a between-group difference of 20% and a usual care responder rate of 20%, we need to include 150 patients in each group. To account for a possible drop-out rate of 25% due to the digital nature of the study, a total of 376 patients are needed.

More detailed information is available in the study protocol [12].

2.4 Statistical Framework

2.4.1 Hypothesis Test

This trial is designed to assess if using the Happy Hands app in addition to usual care is superior to usual care alone with regards to probability of OMERACT/OARSI response at 3 months.

 The primary null hypothesis posits that there is no difference in probability of OMERACT/OARSI response between Happy Hands in addition to usual care compared to usual care alone at 3 months.

> Statistical Analysis Plan Happy Hands Diakonhjemmet Hospital

Page 8 of 27

• The primary alternative hypothesis is that using the Happy Hands app in addition to usual care is superior to usual care alone with regards to probability of OMERACT/OARSI response at 3 months.

2.4.2 Secondary hypotheses

Key secondary hypotheses:

- a) To assess the effect of using the Happy Hands app in addition to usual care compared to usual care only with regards to probability of OMERACT-OARSI response at 6 months.
 - The null hypothesis posits that there is no difference in probability of OMERACT/OARSI response between using Happy Hands in addition to usual care compared to usual care alone at 6 months.
 - The alternative hypothesis is that using Happy Hands in addition to usual care is superior to usual care alone with regards to probability of OMERACT/OARSI response at 6 months.
- b) To assess the cost-effectiveness of using the Happy Hands app in addition to usual care compared to usual care alone at 6 months.
 - The null hypothesis is that the Happy Hands intervention is not cost-effective compared to usual care alone at 6 months.
 - The alternative hypothesis is that using the Happy Hands app is cost-effective compared to usual care alone at 6 months.
- c) To assess the effect of using the Happy in addition to usual care compared to usual care alone on the change in pain from baseline to 3 months.
 - The null hypothesis is that there is no difference in change in pain from baseline to 3 months follow-up between using Happy Hands in addition to usual care compared to usual care alone.
 - The alternative hypothesis is that using the Happy Hands app in addition to usual care in more effective regarding change in pain from baseline to 3 months follow-up compared to usual care alone.
- d) To assess the effect of using the Happy in addition to usual care compared to usual care alone on the change in function from baseline to 3 months.
 - The null hypothesis is that there is no difference in change in function from baseline to 3 months follow-up between using Happy Hands in addition to usual care compared to usual care alone.
 - The alternative hypothesis is that using the Happy Hands app in addition to usual care in more effective regarding change in function from baseline to 3 months follow-up compared to usual care alone.

Additional secondary hypotheses:

a) To assess the effect of using the Happy in addition to usual care compared to usual care alone on the change in grip strength from baseline to 3 months.

Statistical Analysis Plan Happy Hands Diakonhjemmet Hospital

Page 9 of 27

- The null hypothesis is that there is no difference in change in grip strength from baseline to 3 months follow-up between using Happy Hands in addition to usual care compared to usual care alone.
- The alternative hypothesis is that using the Happy Hands app in addition to usual care in more effective regarding change in grip strength from baseline to 3 months follow-up compared to usual care alone.
- b) To assess the effect of using the Happy in addition to usual care compared to usual care alone on the change in disease activity from baseline to 3 months.
 - The null hypothesis is that there is no difference in change in disease activity from baseline to 3 months follow-up between using Happy Hands in addition to usual care compared to usual care alone.
 - The alternative hypothesis is that using the Happy Hands app in addition to usual care in more effective regarding change in disease activity from baseline to 3 months follow-up compared to usual care alone.
- c) To assess the effect of using the Happy in addition to usual care compared to usual care alone on the change in quality of care from baseline to 3 months.
 - The null hypothesis is that there is no difference in change in quality of care from baseline to 3 months follow-up between using Happy Hands in addition to usual care compared to usual care alone.
 - The alternative hypothesis is that using the Happy Hands app in addition to usual care in more effective regarding change in quality of care from baseline to 3 months follow-up compared to usual care alone.
- d) To assess the effect of using the Happy in addition to usual care compared to usual care alone on the change in pain from baseline to 6 months.
 - The null hypothesis is that there is no difference in change in pain from baseline to 6 months follow-up between using Happy Hands in addition to usual care compared to usual care alone.
 - The alternative hypothesis is that using the Happy Hands app in addition to usual care in more effective regarding change in pain from baseline to 6 months follow-up compared to usual care alone.
- e) To assess the effect of using the Happy in addition to usual care compared to usual care alone on the change in function from baseline to 6 months.
 - The null hypothesis is that there is no difference in change in function from baseline to 6 months follow-up between using Happy Hands in addition to usual care compared to usual care alone.
 - The alternative hypothesis is that using the Happy Hands app in addition to usual care in more effective regarding change in function from baseline to 6 months follow-up compared to usual care alone.
- f) To assess the effect of using the Happy in addition to usual care compared to usual care alone on the change in grip strength from baseline to 6 months.
 - The null hypothesis is that there is no difference in change in grip strength from baseline to 6 months follow-up between using Happy Hands in addition to usual care compared to usual care alone.

Statistical Analysis Plan Happy Hands Diakonhjemmet Hospital

Page 10 of 27

- The alternative hypothesis is that using the Happy Hands app in addition to usual care in more effective regarding change in grip strength from baseline to 6 months follow-up compared to usual care alone.
- g) To assess the effect of using the Happy in addition to usual care compared to usual care alone on the change in disease activity from baseline to 6 months.
 - The null hypothesis is that there is no difference in change in disease activity from baseline to 6 months follow-up between using Happy Hands in addition to usual care compared to usual care alone.
 - The alternative hypothesis is that using the Happy Hands app in addition to usual care in more effective regarding change in disease activity from baseline to 6 months follow-up compared to usual care alone.
- h) To assess the effect of using the Happy in addition to usual care compared to usual care alone on the change in quality of care from baseline to 6 months.
 - The null hypothesis is that there is no difference in change in quality of care from baseline to 6 months follow-up between using Happy Hands in addition to usual care compared to usual care alone.
 - The alternative hypothesis is that using the Happy Hands app in addition to usual care in more effective regarding change in quality of care from baseline to 6 months follow-up compared to usual care alone.

2.4.3 Other objectives

Other objectives are considered to be supportive or exploratory, thus, they are not subject to hypothesis testing.

2.4.4 Decision Rule

For the primary outcome, superiority of probability of OMERACT/OARSI response is claimed if the null hypothesis is rejected at the significance level (alpha) of 0.01 (Bonferroni corrected due to multiple testing of one primary and four key secondary hypotheses; 0.05/5= 0.01. The result is deemed clinically relevant if the lower limit of the 95% confidence interval is more than 20% (see figure 2).

A significance level of <0.01 will also be used for the four key secondary hypotheses due to multiple testing.

For the additional secondary outcomes, multiple testing adjustment will not be carried out. The listed hypotheses will be assessed by their (unadjusted) p-values though no formal acceptance/rejection of these hypotheses will be done.

The intervention will be considered cost-effective if the incremental cost effectiveness ratio is below the threshold for cost-effectiveness, recommended in Norway. In the health economic evaluation, we will not consider p-values or confidence intervals for the ICER but instead plot bootstrapped ICERs on the cost-effectiveness plane and calculate a cost-effectiveness acceptability curve [16].

Statistical Analysis Plan Happy Hands Diakonhjemmet Hospital

Page 11 of 27

Figure 2: Visualization of superiority and clinically relevant difference.

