5.2.2 Secondary Outcomes

5.2.2.1 Secondary Analyses

a) OMERACT/OARSI responders at 6 months
For the secondary outcome of probability of OMERACT/OARSI response in the two groups at 6 months, we will conduct the same analysis as for the primary outcome.

Secondary continuous outcomes will be analysed using linear regression. The analyses will, in addition to randomization group, adjust for baseline level of the outcome and study center. Missing values will be handled using multiple imputation.

b) Health economic evaluation

Aim: To assess whether the Happy Hands app in combination with usual care is a cost-effective treatment strategy for patients with hand OA compared to usual care alone.

Statistical software: Mainly STATA. Excel for bootstrap, plotting results on the cost-effectiveness plane and for construction the cost-effectiveness acceptability curve.

Perspective on costs: health care perspective as primary analysis, inclusion of production loss in explorative analysis.

Cost of the intervention: The Happy Hands app is not yet commercially available, hence has no official list price or yearly fee. Based on the cost of development and maintenance and the size of the eligible patient population, we assume that the app will be offered at an annual subscription fee of NOK 150 (EUR 13).

Identification of resources: patient self-reported in questionnaire, asked about resource use items as displayed in Table 1.

Measurement of resource use: patient self-reported in questionnaire. May add information from clinical expertise if needed, e.g. patient reports a rehabilitation stay, but not duration.

Statistical Analysis Plan Happy Hands Diakonhjemmet Hospital

Page 22 of 27

Valuation of resource use data: As far as possible, we will use unit prices reported in the Directorate of Medical Products database for use in health technology assessments (https://view.officeapps.live.com/op/view.aspx?src=https%3A%2F%2Fwww.dmp.no%2Fglobalassets %2Fdocuments%2Foffentlig-finansiering-og-pris%2Fdokumentasjon-tilmetodevurdering%2Fenhetskostnader-v1.5.xlsx&wdOrigin=BROWSELINK), this includes the price per in-patient day at hospital.

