If some unit price is not available in this database, we will use publicly available reimbursement rates. For visits to an occupational therapist in primary care, we will assume an average duration of visit and wage of therapist. Medical and technical equipment, such as a bread knife or vegetable knife with built-up handles, key for opening jars, or self-opening scissors, will be based on market prices (e.g. https://www.velferdsbutikken.no/categories/hjelpemidler-kjokken).

Identification of outcomes: self-reported in questionnaires.

Measurement of outcomes: Health related quality of life measured by the EQ-5D-5L. In the analysis of EQ-5D-5L, we will adjust for baseline imbalances using the method recommended by Manca and co-workers [26], if warranted.

Valuation of outcomes: Primary analysis based on the Norwegian EQ-5D-5L tariff by Garratt and cocorkers [27], sensitivity analysis with the UK Devlin tariff [28].

Analysis population: primary analysis with ITT population, may explore PP as sensitivity analysis.

Timing: Health-related quality of life is measured at baseline, 3 and 6 months, while costs are measured at 3 and 6 months.

Discounting: not relevant due to trial duration

Cost-effectiveness threshold: threshold suggested for Norway at time of analysis, currently NOK, 275,000 per QALY for patients with osteoarthritis

Statistical decision rule: Cost-effective if incremental cost-effectiveness ratio below threshold and if intervention has a higher probability of being cost-effective than comparator based on bootstrap results.

Analysis of resource use: mean cost per patient reported in 2024 EUR, will use valuta converter provided by "Norges Bank" to convert NOK to EUR using the average exchange rate in 2024 (https://www.norges-bank.no/tema/Statistikk/valutakurser/?tab=currency&frequencyTab=3).

Analysis of outcomes: mean QALY per patient. We expect no effect on mortality, hence any QALY gain will be a result of improvements in function and well-being. QALYs will be calculated based on the area under the curve approach. We will assume that transition between different health utility values will take place halfway between two measurements.

Missing data: if whole questionnaire of EQ-5D-5L is missing, multiple imputation, if single questions are missing, simple imputation. Costs are assumed to be missing only if the whole questionnaire is missing, if the questionnaire is missing, we will impute using multiple imputation.

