Statistical Analysis Plan Happy Hands Diakonhjemmet Hospital

Page 23 of 27

Analysis of cost-effectiveness: ICER=difference in mean costs/difference in mean QALY

Sampling uncertainty: We will use non-parametric bootstrapping to assess the degree of uncertainty around the ICER. We bootstrap costs and QALY 10,000 times with replacement, recalculate ICERS and plot the results on the cost-effectiveness plane. The likelihood of cost-effectiveness will then be calculated as the proportion of all bootstrapped samples below the cost-effectiveness threshold value. A cost-effectiveness acceptability curve will be constructed to illustrate how sensitive the conclusion is to varying levels of threshold values. This approach is one of several alternatives recommended for trial-based cost-effectiveness analyses [16].

Subgroup analysis: Per protocol population

Sensitivity analysis: Devlin tariff for the EQ-5D-5L

Explorative analysis: including loss of production

c) Effect on secondary outcomes (pain, hand function, grip strength, disease activity and guality of care)

To assess the effect of using the Happy Hands app in addition to usual care compared to usual care only on secondary outcomes of pain, hand function, grip strength, disease activity and quality of care, we will use multiple linear regression with the mean change scores at 3 and 6 months as dependent variables and group as independent variable, adjusting for baseline values for the variable of interest and recruitment sites.

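### The ICER-below-threshold rule has no condition on the sign of the QALY difference, so as written it passes an app that costs more and yields fewer QALYs

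*SAP*

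**What the plan says.** Cost-effectiveness at 6 months is key secondary hypothesis b) in SAP section 2.4.2. The rule for it appears in two places.

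- **Section 2.4.4, Decision Rule**, has one condition: "The intervention will be considered cost-effective if the incremental cost effectiveness ratio is below the threshold for cost-effectiveness, recommended in Norway".
- **Section 5.2.2.1 b), Statistical decision rule**, has two: "Cost-effective if incremental cost-effectiveness ratio below threshold and if intervention has a higher probability of being cost-effective than comparator", the second judged on the bootstrap results.

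The quantities come from the same part of section 5.2.2.1 b). The ratio is "ICER=difference in mean costs/difference in mean QALY". The current threshold is NOK "275,000 per QALY for patients with osteoarthritis". For sampling uncertainty, costs and QALYs are resampled 10,000 times, the ICERs are recalculated and plotted on the cost-effectiveness plane, and: "The likelihood of cost-effectiveness will then be calculated as the proportion of all bootstrapped samples below the cost-effectiveness threshold value".

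Section 2.4.4 also says: "A significance level of <0.01 will also be used for the four key secondary hypotheses due to multiple testing". Two paragraphs later it says of the health economic evaluation that "we will not consider p-values or confidence intervals for the ICER".

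**The concern.** An ICER carries no information about which quadrant of the cost-effectiveness plane it comes from. A negative value can mean cheaper and better, or dearer and worse. A positive value can mean a price paid per QALY gained, or a saving per QALY given up. Comparing the ratio with a threshold is therefore a valid decision rule only when the QALY difference is positive, and the SAP sets no such condition.

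The case is realistic. Follow-up is 6 months, no mortality effect is expected, and the app is priced at NOK 150 a year, so both differences may lie close to zero. Bootstrap draws would then fall in all four quadrants. If the text is programmed as written, the yes/no conclusion can be wrong, and the reported probability and the acceptability curve inherit the same miscount.

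**Working it through.** The SAP gives no figure of its own to reproduce here; the check is of the rule's logic.

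**Inputs from the SAP.** Threshold L = NOK 275,000 per QALY and annual app fee NOK 150 (both section 5.2.2.1 b). Write dC for the difference in mean cost and dQ for the difference in mean QALYs. Then ICER = dC/dQ, and incremental net monetary benefit NMB = L × dQ − dC. The app is worth its cost at threshold L when NMB > 0.

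**Step 1: algebra.**
- If dQ > 0, dC/dQ < L is the same as dC < L × dQ, that is NMB > 0. The rule is right.
- If dQ < 0, multiplying by dQ turns the inequality round: dC/dQ < L is the same as dC > L × dQ, that is NMB < 0. The rule passes exactly the cases that should fail.

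This needs no assumption about variability.

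**Step 2: examples at L = 275,000.**

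| dC (NOK) | dQ | ICER | Rule as written | NMB = 275,000 × dQ − dC | By NMB |
|---|---|---|---|---|---|
| +500 | -0.01 | -50,000 | pass | -2,750 − 500 = -3,250 | fail (dominated) |
| +150 | -0.005 | -30,000 | pass | -1,375 − 150 = -1,525 | fail (dominated) |
| -500 | -0.01 | +50,000 | pass | -2,750 + 500 = -2,250 | fail |
| -5,000 | -0.01 | +500,000 | fail | -2,750 + 5,000 = +2,250 | pass |
| +1,000 | +0.01 | +100,000 | pass | 2,750 − 1,000 = +1,750 | pass |

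**Step 3: the bootstrap probability.** The SAP gives no standard errors, so the following are assumptions: SE of dQ 0.0072 (varied from 0.004 to 0.012), SE of dC NOK 500 to 1,500, true dC NOK 150 (the full annual fee, other costs equal), and dC and dQ independent and normal. The literal count is the share of draws with dC/dQ < L. The correct count is the share with NMB > 0, in closed form Φ((L × dQ − 150) / √((L × SE_Q)² + SE_C²)). Simulated shares from 1,000,000 draws per scenario agree with the closed form to within 0.001.

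Results for SE of dQ 0.0072; each range runs over the two cost SEs:

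| True dQ | Literal ICER count | Share with NMB > 0 |
|---|---|---|
| -0.01 | 91%-97% | 8%-12% |
| -0.005 | 83%-94% | 23%-27% |
| 0 | 79%-92% | 47%-48% |
| +0.005 | 82%-93% | 69%-73% |
| +0.01 | 89%-96% | 85%-90% |
| +0.02 | 98.5%-99.8% | 98.4%-99.6% |

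With SE of dQ from 0.004 to 0.012, the figures at dQ = 0 are 70%-95% against 45%-48%. At +0.01 the gap runs from almost nothing to 18 points. At +0.02 with SE 0.012 it is 3 to 4 points.

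**Step 4: a patient-level bootstrap.** Assumptions: 150 per arm, cost SD NOK 6,000, 6-month QALY SD 0.06, costs and QALYs uncorrelated, 10,000 resamples. A dominated result of +NOK 1,000 and -0.01 QALY had 95% of resamples with an ICER below the threshold value, against 3% with positive net benefit.

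**Step 5: the second condition in section 5.2.2.1 b).** Counted on the ICER value, with the comparator's probability taken as one minus the app's, it changed no decision in 1,500 simulated trials in each of 12 scenarios. At a true dQ of -0.005 the pass rates were 0.935 and 0.833 for the two cost SEs, with or without the condition. By net benefit they were 0.247 and 0.265.

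**The case against.** The strongest reply is that the text can be read in a valid way. The sampling-uncertainty paragraph plots the results on the plane and then counts samples, not ICERs. Points below the threshold line on that plane is a natural meaning, and it equals NMB > 0. On that reading the second condition does block a dominated app: at a true dQ of -0.01 the net-benefit share is only 8%-12%, well below one half. The simulation in step 5 assumes the literal count, so it shows what that count does and is not evidence that it will be used. An analyst looking at the plot would also probably notice a cloud with fewer QALYs.

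That reading is possible, but the SAP speaks of recalculated ICERs and a threshold value, and never of a line or quadrant. It can rescue only the bootstrap count and, through it, the second condition. It does not rescue section 2.4.4, which has the single condition and no bootstrap element. The plot is not tied to the decision, and a bootstrap planned in Excel invites a direct ratio-below-threshold count.

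The percentages do rest on assumed standard errors and on independence of costs and QALYs, and they illustrate what happens if the literal rule is programmed. Charging the full annual fee to a 6-month comparison is also a choice. Halving it to NOK 75 moves the net-benefit share at dQ = 0 from about 47% to 48.5% (SE of dQ 0.0072, SE of dC NOK 500), and by at most about 2.5 points at the smallest SEs. At dQ = 0 the correct answer is close to even, so the error there is mainly false confidence; the clear reversals are where QALYs are lost.

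**Conclusion.** The concern holds. As written, the decision rule for a key secondary hypothesis gives the wrong answer whenever the QALY difference is negative. That follows from the algebra alone. How much the bootstrap probability is inflated depends on the assumed standard errors: very large when the true QALY difference is zero or below, moderate for small gains, and negligible for a clear gain unless the QALY difference is imprecise. Whether the error would reach the report depends on how the analysts read the text, and the SAP should not leave that open. The primary outcome is untouched.

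Two smaller wording points belong with it. Sections 2.4.4 and 5.2.2.1 b) give one condition and two, and should agree. Section 2.4.4 promises the 0.01 level for four key secondary hypotheses but gives cost-effectiveness no p-value. That is only conservative: the primary and three tested key secondary hypotheses spend 4 × 0.01 = 0.04 of the 0.05.

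**What to change.** Put one rule in section 2.4.4 and in the statistical decision rule and sampling-uncertainty entries of section 5.2.2.1 b), for example:

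> The app is cost-effective if the mean incremental net monetary benefit (threshold × QALY difference − cost difference) is above 0. The probability of cost-effectiveness is the share of bootstrap draws with net monetary benefit above 0, and the acceptability curve is this share at each threshold.

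The ICER can still be reported, with its quadrant stated. On the point estimates the new rule gives the same verdict as the ICER rule whenever QALYs rise, and it corrects the verdict when they fall. A sentence defining the count as draws below the threshold line on the plane would repair the bootstrap part, but section 2.4.4 would still need its own sign or quadrant condition. In section 2.4.4, limit the 0.01 sentence to the three key secondary hypotheses that are tested; the level itself can stay.

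The cost is a sentence in each of three places and one extra column in the bootstrap sheet, with no new data and no change to alpha or sample size.
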